15.0 Drug Information

15.1 AZD1775

- 15.11 **Background:** AZD1775 is a highly selective, adenosine-triphosphate (ATP) competitive, small molecule inhibitor of Wee1 kinase, that is involved in regulation of intra-S and G2 cell cycle checkpoints through phosphorylation and inhibition of CDK2 and CDK1, respectively. AZD1775 has significant selectivity over other tested protein kinases. In vitro, AZD1775 inhibits Wee1 activity and induces DNA damage as well as G2 checkpoint escape in cell based assays. AZD1775 increases cytotoxicity when used in combination with DNA damaging agents, such as gemcitabine, cisplatin, carboplatin and topotecan, in p53-deficient cell lines. In vivo, AZD1775 was well tolerated and showed enhancement of anti-tumor efficacy by gemcitabine, carboplatin, cisplatin, 5-fluorouracil (5-FU) and capecitabine in nude rat xenograft tumor models. Similarly, in nude mouse xenograft models, AZD1775 treatment resulted in significant tumor growth inhibition at tolerated doses, and also enhanced the anti-tumor growth effect of gemcitabine, carboplatin, and radiation therapy.
- 15.12 **Formulation:** AZD1775 is currently available as dry filled capsules for oral administration containing AZD1775 with the following excipients: lactose, microcrystalline cellulose, croscarmellose sodium, and magnesium stearate.
- 15.13 **Preparation and storage:** Capsules are packaged in high density polyethylene (HDPE) bottles, and should be stored at room temperature, no more than 30° C. For further information, refer to the investigational product label. Provided by AstraZeneca.
- 15.14 **Administration:** 300 mg PO (or respective dose) once daily either 2 hours before or 2 hours after a meal
- 15.15 **Pharmacokinetic information:** The PK data of AZD1775 following a single oral administration showed a moderate rate of absorption with a Tmax occurring at 3 to 4 hours. Post-peak plasma concentrations declined essentially in a mono-exponential manner with a t1/2 in the region of 10 hours. Exposure as measured by maximum plasma drug concentration observed (Cmax) and area under the curve (AUC)0-∞ increased in a dose-proportional manner over the dose range of 325 to 1300 mg. Following single (100 to 325 mg) and multiple dose administrations of AZD1775 (25 to 325 mg BID and 100 to 200 mg once daily [QD]) with carboplatin, cisplatin, and gemcitabine, plasma exposure of AZD1775 was consistent with predictions based on the single-dose regimen. AZD1775 was moderately bound to plasma proteins in all species tested, with the unbound fractions (at AZD1775 concentration of 1 µM) in plasma from the rat, dog and human being 23.2, 40.0, and 39.5%, respectively. Binding

to plasma proteins was independent of AZD1775 concentration (0.1-10 μM) in the rat and human, but an increase in unbound fraction from 30.6% at 0.1 μM to 45.4% at 10 μM was observed in the dog. CYP3A4 is the major CYP isoform involved in the oxidative metabolism of AZD1775, to the N-demethylated product. In addition, studies with flavin-containing monooxygenase (FMO) enzymes indicated that FMO3 and FMO5 were involved in formation of the N-oxide derivative of AZD1775.

15.16 **Potential Drug Interactions:** The following treatments and all the medications listed in Appendix VI are prohibited while in this study. Any further questions regarding concomitant treatments should be referred to the sponsor:

- No other investigational therapy should be given to patients. No anticancer agents other than the study medications should be given to patients. If such agents are required for a patient, then the patient must first be withdrawn from the study.
- No formal clinical drug interaction studies have been performed with AZD1775. An exploratory assessment of the effect of aprepitant on AZD1775 exposure in oncology patients suggests that there is a drug interaction between AZD1775 and aprepitant, as exposure to AZD1775 increased by 40% when aprepitant was co-administered with AZD1775. The observed increase in AZD1775 exposure is likely the result of CYP3A4 inhibition by aprepitant. This increase in exposure is statistically significant. At the selected MTDs, this increase may also be of clinical importance. Therefore, concomitant treatment with aprepitant and fosaprepitant is not allowable per protocol until further evaluation.

Potent or moderate inhibitors or inducers of CYP3A4, sensitive CYP3A4 substrates, and CYP3A4 substrates with a narrow therapeutic window should be avoided until additional data on drug-drug interaction becomes available (Appendix VI).

- *In vitro* data suggests that AZD1775 may also be a weak reversible inhibitor of CYP2C19. Caution should be exercised with concomitant administration of AZD1775 and agents that are sensitive substrates of CYP2C19, or substrates of this enzyme with narrow therapeutic range; refer to Appendix VI for a list of sensitive substrates of CYP2C19, or substrates of this enzyme with narrow therapeutic range.
- AZD1775 has been shown to be a weak inducer of CYP1A2 *in vitro* with a maximum measured response between donors of 39.9% to 93.1% (at 10 μM) and 18.6% to 32.5% (at 5 μM) of the positive control omeprazole (50 μM), respectively. Given the nature of the AZD1775 dosing schedule, however, the risk of induction in the clinic is considered low. No specific precautions or change in medications are recommended at this time, except to be initially vigilant when using substrates of CYP1A2 with a narrow therapeutic range.
- *In vitro* studies have shown that AZD1775 may be a substrate and inhibitor for human P-glycoprotein (P-gp). Caution should be exercised when agents that are inhibitors or substrates of P-gp are administered concomitantly with AZD1775 (see Appendix VI).

- Recent *in vitro* transporter studies have shown AZD1775 to be an inhibitor of BCRP (IC₅₀ 5.1 μM). This finding is particularly relevant for drugs administered orally where exposure is normally limited by BCRP-mediated efflux, in particular some statins. Modelling has predicted a substantial increase in the exposure of Atorvastatin when co-administered with AZD1775 and the **use of Atorvastatin is therefore prohibited** in the current study. Other drugs where the disposition is mediated via BCRP should be administered with caution, dose modification considered or substituted by an alternative drug (Appendix VI).
- AZD1775 has been shown to be an inhibitor of MATE1 and MATE2K transporters. A drug interaction with substrates of either transporter cannot be ruled out, the most important substrate known to date being **metformin**. Thus patients taking these medication should be carefully monitored for their glycemic control. Patients on metformin should be closely watched for elevated metformin levels that could put them at risk for hypoglycemia.
- Herbal preparations/medications are not allowed throughout the study. These herbal medications include, but are not limited to: St. John's wort, kava, ephedra (ma huang), ginkgo biloba, dehydroepiandrosterone (DHEA), yohimbe, saw palmetto, and ginseng. Patients should stop using these herbal medications 14 days prior to first dose of AZD1775.

15.17 **Known potential toxicities:** Based on the preliminary safety data available, the most frequent adverse events observed were blood and lymphatic disorders (anemia, febrile neutropenia), gastrointestinal disorders (diarrhea, vomiting, nausea, abdominal pain, constipation), general disorders and administration site conditions (fatigue, fever, chills), and investigation findings (thrombocytopenia, neutropenia, hematology and serum chemistry).

15.18 **Drug procurement:** Drug will be provided by AstraZeneca.

15.2 Cytarabine (AraC)

15.21 **Background:** Cytarabine (cytosine arabinoside) inhibits DNA synthesis. Cytosine gains entry into cells by a carrier process, and then must be converted to its active compound, aracytidine triphosphate. Cytosine is a pyrimidine analog and is incorporated into DNA; however, the primary action is inhibition of DNA polymerase resulting in decreased DNA synthesis and repair. Cytarabine is specific for the S phase of the cell cycle (blocks progression from the G1 to the S phase).

15.22 **Formulation:** Commercially available for injection, powder for reconstitution: 100 mg, 500 mg, 1 gram, 2 gram

- 15.23 **Preparation, storage, and stability:** Store intact vials of powder at room temperature 15°C to 30°C (59°F to 86°F). Reconstitute with bacteriostatic water for injection. Reconstituted solutions are stable for up to 8 days at room temperature, although the manufacturer recommends use within 48 hours. Further dilution in 250-1000 mL of D5W or 0.9% NaCl is stable for 8 days at room temperature (25°C). Note: Solutions containing bacteriostatic agents should not be used for the preparation of either high doses or intrathecal doses of cytarabine.
- 15.24 **Administration:** Low-dose cytarabine (LD-AraC) will be administered at a starting dose of 20 mg BID subcutaneously (sc) for 10 days of a 28-day cycle., with dosing adjustments as outlined in section 8.
- 15.25 **Pharmacokinetic information:**
Distribution: V_d: Total body water; widely and rapidly since it enters the cells readily; crosses blood-brain barrier with CSF levels of 40% to 50% of plasma level
Metabolism: Primarily hepatic; metabolized by deoxycytidine kinase and other nucleotide kinases to aracytidine triphosphate (active); about 86% to 96% of dose is metabolized to inactive uracil arabinoside.
Half-life elimination: I.V.: Initial: 7-20 minutes; Terminal: 1-3 hours.
Excretion: Urine (~80%) within 24 hours.
- 15.26 **Potential Drug Interactions:**
Decreased Effect: Cytarabine may decrease the effect of Flucytosine; cytarabine may decrease digoxin absorption.
- 15.27 **Known potential adverse events:** Consult the package insert for the most current and complete information.
Warnings/Precautions: Potent Myelosuppressive agent
Common known potential toxicities, frequency not defined:
 Other: Fever
 Dermatologic: Rash
 Gastrointestinal: Anal inflammation, anal ulceration, anorexia, diarrhea, mucositis, nausea, vomiting
 Hematologic: Myelosuppression, neutropenia, anemia, thrombocytopenia, bleeding, leukopenia, megaloblastosis, reticulocytes decreased
 Hepatic: Hepatic dysfunction, transaminases increased (acute)
 Local: Thrombophlebitis

Less common known potential toxicities:
 Cardiovascular: Chest pain, pericarditis
 Central nervous system: Dizziness, headache, neural toxicity, neuritis
 Dermatologic: Alopecia, pruritus, skin freckling, skin ulceration, urticaria
 Gastrointestinal: Abdominal pain, bowel necrosis, esophageal ulceration, esophagitis, pancreatitis, sore throat
 Genitourinary: Urinary retention
 Hepatic: Jaundice
 Local: Injection site cellulitis

Ocular: Conjunctivitis
 Renal: Renal dysfunction
 Respiratory: Dyspnea
 Miscellaneous: Allergic edema, anaphylaxis, sepsis

Infrequent and/or case reports:

Amylase increased, aseptic meningitis, cardiopulmonary arrest (acute), cerebral dysfunction, cytarabine syndrome (bone pain, chest pain, conjunctivitis, fever, maculopapular rash, malaise, myalgia); exanthematous pustulosis, hyperuricemia, injection site inflammation (SubQ injection), injection site pain (SubQ injection), interstitial pneumonitis, lipase increased, paralysis, rhabdomyolysis, veno-occlusive liver disease

- 15.28 **Drug procurement:** Commercial supplies. Pharmacies or clinics shall obtain supplies from normal commercial supply chain or wholesaler.

16.0 Statistical Considerations and Methodology

16.1 Overview:

This study is a phase II screening study. It is divided into two portions. The safety portion is designed to determine the dose of the treatment agents. The expansion portion is designed to continue enrollment at the acceptable dose levels to determine efficacy of treatment in the patient cohorts of the respective study criteria. (Arm A: AZD1775 days 1-5 & 8-12) and AraC days 1-5 & 8-12) and to make a selection of one of the two randomized arms for Relapsed/Refractory AML and HMA failure MDS/ AML patients (Arm B: AZD1775 days 1-5 & 8-12) and AraC days 1-5 & 8-12; Arm C: AZD1775 days 1-5, 8-12). In addition on Arm C single agent AZD1775, a cohort of n=7 MF patients will be treated to obtain pilot efficacy data. These MF patients will not be formally included in the statistical calculations for Arm C.

The purpose of this screening design is NOT TO ensure a high probability that the very best treatment is selected, but to ensure a low probability that a poor treatment is selected. In other words, at the conclusion of this trial, we cannot make a definitive conclusion about the superiority of one treatment compared to the other, but we can ensure that there is a small probability of bringing the inferior treatment forward.

16.2 Statistical Design and Analysis for the Primary Endpoint

16.21 Primary Endpoint

The primary endpoint of this trial is the rate of complete response (CR plus CRi). Throughout Section 16.0, complete response will be considered synonymous with “success”, unless specified otherwise. All patients meeting the eligibility criteria, who have signed a consent form, and have begun treatment at the study MTD will be evaluable for complete response, with the exception of patients who are determined to be a major treatment violation.

Treatment Responses will be assessed by standard criteria for the respective disease per NCCN guidelines or according to specific criteria from expert panels (i.e. the International Working Group Criteria for the response in acute myeloid leukemias). Response will be assessed by peripheral blood criteria at the end of each cycle and every other cycle (for MDS) thereafter (Burnett et al. 2007, Gileset al. 2005, Kantarijian et al. 2012, Fenaux et al. 2009). Bone marrow tests to assess responses will be carried as outlined in the study tables Table 4.1 and 4.2.

16.22 Arm A: Efficacy and safety of AZD1775 + AraC in elderly newly diagnosed AML

Statistical Design, Analysis and Decision Rule

Efficacy and safety of AZD1775 + AraC will be tested in elderly patients with newly diagnosed AML using a single-arm single-stage binomial design. The primary endpoint will be the complete response rate, which will be defined as an objective status of CR or CRi. Complete response rate will be evaluated over all cycles of study treatment. The proportion of CR/CRi responses will be estimated by the number of CR/CRi responses divided by the total number of evaluable patients. Two-sided 95% confidence intervals will be computed using an exact binomial confidence interval. The frequency and relative frequency of individual response categories will also be computed. For a subject to be considered evaluable for statistical analysis, the subject must be eligible, provide consent, initiate treatment and not experience a major treatment violation during the first cycle of treatment.

The largest CR/CRi response proportion where the proposed treatment regimen would be considered ineffective in this population is 15% (Burnett et al. 2007, Gileset al. 2005, Kantarijian et al. 2012, Fenaux et al. 2009) and the smallest CR/CRi response proportion that would warrant subsequent studies with the proposed regimen in this patient population is 40%.

The following one-stage binomial design uses 21 patients to test the null hypothesis that the true CR/CRi response proportion in a given patient population is at most 15%.

Decision Rule: Enter 21 patients into the study. If 5 or fewer CR/CRi responses are observed in the first 21 evaluable patients, we will consider this regimen ineffective in this patient population. Otherwise, if 6 or more CR/CRi responses are observed in the first 21 evaluable patients, we may recommend further testing of this regimen in subsequent studies in this population. We anticipate accruing an additional 2 patients to account for ineligibility, cancellation, major treatment violation, or other reasons. Thus, the total maximum accrual to this arm is 23 patients.

Assuming that the number of CR/CRi responses is binomially distributed, the significance level within this arm is $\leq 10\%$ and the probability of declaring that this regimen warrants further studies (i.e., statistical power) under various

CR/CRi response proportions can be tabulated as a function of the true CR/CRi response rate as shown in the following table.

If the true CR/CRi rate is...	0.15	0.20	0.25	0.30	0.35	0.40
Then the probability of declaring that the regimen warrants further studies is...	0.08	0.23	0.43	0.64	0.80	0.90

- 16.23 Arm B and C: Efficacy and safety of AZD1775 in combination with AraC compared to AZD1775 alone in relapsed/refractory AML or HMA failure MDS and AML patients.

Statistical Design, Analysis and Decision Rule

Efficacy and safety of AZD1775 alone or with AraC will be tested in patients with relapsed/refractory AML and patients with HMA failure MDS using a flexible randomized phase II selection design. Patients will be randomized to AZD1775 alone or with AraC in a 1:1 fashion using a dynamic allocation procedure (Pocock & Simon 1975). The primary endpoint will be the complete response rate, which will be defined as an objective status of CR or CRi. Complete response rate will be evaluated over all cycles of study treatment. The proportion of CR/CRi responses will be estimated by the number of CR/CRi responses divided by the total number of evaluable patients (by arm). Two-sided 95% confidence intervals will be computed using an exact binomial confidence interval. The frequency and relative frequency of individual response categories will also be computed. Estimates will also be computed by arm separately for each disease. For a subject to be considered evaluable for statistical analysis, the subject must be eligible, provide consent, initiate treatment and not experience a major treatment violation during the first cycle of treatment.

The selected design is a flexible randomized phase II selection design (Sargent & Goldberg 2001). This study will randomize 40 evaluable patients (20 per arm). The minimum required number of CR/CRi responses for an arm to be considered as having evidence of efficacy is 3 (out of 20 evaluable patients). This decision rule is based on a single-arm single-stage binomial design testing the null hypothesis that the true CR/CRi response proportion in a given arm is at most 5% (Tawfik et al. 2014, Giles et al. 2005, Jabour et al. 2010, Prevet et al. 2011) with the smallest CR/CRi response proportion warranting subsequent studies being 25%.

In the event that both arms meet this decision rule for efficacy, the combination arm will be considered as having additional efficacy over the single-agent arm if the CR/CRi response rate on the combination arm is at least 10% greater than the single-agent arm. If the difference is <10%, then the trial is considered statistically ambiguous and the selection between the combination and single-agent arm will be allowed to include other factors (e.g., adverse event data) in addition to the CR/CRi response rate. We anticipate accruing an additional 4 patients (2 patients per arm) to account for ineligibility, cancellation, major

treatment violation, or other reasons. Thus, the total maximum accrual to Arm B is 22 patients and to Arm C is 22 patients.

Assuming that the number of CR/CRi responses is binomially distributed, the significance level for the single-arm decision rule requiring a minimum of 3 (out of 20 evaluable patients) within an arm is $\leq 10\%$ and the probability of declaring that a given arm's treatment regimen warrants further studies (i.e., statistical power) under various CR/CRi response proportions can be tabulated as a function of the true CR/CRi response rate as shown in the following table.

If the true CR/CRi rate is...	0.05	0.10	0.15	0.20	0.25
Then the probability of declaring that a given arm's treatment regimen warrants further studies is...	0.08	0.32	0.60	0.79	0.91

Probabilities for the combination arm being selected as the overall winner are provided in the following table.

CR/CRi rate (AZD1775 alone)	CR/CRi rate (AZD1775 + AraC)	Probability combo selected over single-agent arm
0.05	0.05	0.07
0.25	0.25	0.30
0.20	0.25	0.44
0.15	0.25	0.61
0.10	0.25	0.77
0.05	0.25	0.88

16.3 Sample Size, Accrual Rate, and Study Duration

This design is expected to accrue 18 patients to the safety portion with the possibility of enrolling up to 54 + 7 MF patients. Six patients in each of the safety arms will be treated at the MTD and thus will be eligible for primary endpoint analysis. An additional 15 AML patients in Arm A and 14 AML or MDS patients in both arm B and C will be enrolled per treatment arm in the expansion portion with the addition of another 2 per arm to account for ineligibility, cancellation, major treatment violation, or other reasons. Thus the final accrual may be as large as 102 + 7 MF patients or as low as 67 + 7 MF patients (Arm A: 23; Arm B: 22; Arm C: 22 + 7 MF patients).

The anticipated accrual rate is 2-4 evaluable patients per month. Therefore, the accrual period is expected to be approximately 1.5-2.5 years. The primary endpoint will be evaluated approximately 2 years after the trial opens, or after the last patient accrued has been observed for at least 4 months. The total study duration is expected to be approximately 3.5 years.

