Appendix IX – Childbearing Potential & Contraception

Schema

If a patient is deemed ineligible or a does not start first dose of treatment, please refer to Section 13.0 for follow-up information.

Cycle length=28 days

NOTE: The Safety portion of this trial will monitor six patients in each arm (combination and single agent) and observe them for a minimum of 28 days to assess toxicities.

Primary & Secondary MF: Primary Myelofibrosis (PMF) and Secondary MF after Polycythemia Vera (PV) and Essential Thrombocytosis (ET) (post-PV/ post-ET MF)

Generic name: AZD1775, Adavosertib Brand name(s): n/a Availability: Provided by AstraZeneca
	
Generic name: Cytosine arabinoside Brand name(s): Cytosar, ® Availability: Commercially available

--	--

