7.2 Treatment Plan for AZD1775 combined with AraC (Arms A and B)

7.21 Safety Portion

The safety portion of this trial will consist of a limited dose escalation and subsequently assess the safe combination dose of AZD1775 with standard AraC s.c. twice daily dosing. A limited safety run in dose escalation of AZD1775 will be performed as outlined in Table 7.21. Three subjects from either arm will be treated and observed for a minimum of 28 days to assess toxicities. Toxicity and DLT/MTD criteria will follow a classical three by three dose escalation toxicity assessment:

In the run-in portion of the trial, 3 patients who are eligible for the trial will be treated at dose level 0 (AZD1775 200 mg PO once daily and AraC 20 mg s.c. twice daily days 1-5 & 8-12) and observed for a minimum of 28 days. If there are no DLT defining toxicities, the following 3 patients will be treated at dose level 1 (AZD1775 250 mg PO once daily and AraC 20 mg s.c. twice daily days 1-5 & 8-12). If there are no DLT defining toxicities at dose level 1, the next 3 will be treated at dose level 2 (AZD1775 300 mg PO once daily and AraC 20 mg s.c. twice daily days 1-5 & 8-12). If there are no DLTs in the first 3 patients at dose level 2, an additional 3 patients will be treated. If $\leq 1/6$ patients at dose level 2 experience DLT, the Expansion portion (cohort) of the trial will be opened for the remaining patients.

If 1/3 patient experiences a DLT at a given dose level, an additional 3 patients will be enrolled at this dose level. If there are no further DLTs (maximum of $\leq 1/6$ patients with DLT at any given dose level) this dose level will be defined as the MTD dose level and advanced to the Expansion portion of the study. If 2/3 patients experience a DLT, dose will be de-escalated by one dose level and an (additional) 3 patients treated at the next lower dose level, unless six patients have been treated already and there were $\leq 1/6$ DLT, then this level will be defined as MTD dose level and advanced to the Expansion portion. If $\geq 2/6$ patients experience at any dose level, then enrollment into that study arm will be placed on hold, and a meeting of all participating investigators, the NYU DSMC Medical Monitor, the Astra Zeneca Trial/ Program Lead will be called to determine how best to proceed, as well as available PK data will be reviewed.

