If DLT occurs at dose level 0, study will be de-escalated to dose level -1 (AZD1775 150 mg PO once daily and AraC 20 mg s.c. twice daily days 1-5 & 8-12). If $\leq 1/3$ patients have DLT another 3 patients will be enrolled and if $\leq 1/6$ patients have DLT, then this level will be

defined as MTD dose level and advanced to the Expansion portion. If 2/3 patients at dose level -1 have DLT, the combination will be deemed as not tolerable in combination with LD-AraC.

NOTE: the Safety/ Escalation portion and MTD determination for Arm A (newly diagnosed/ untreated AML) and Arm B (relapsed/ refractory AML, HMA failure MDS) as outlined above will be performed together with patients from both Arms eligible. .

Table 7.21: Safety run in dose escalation

Dose Level	AZD1775 ²	Cytarabine (AraC) ¹
-1	150 mg PO once daily days 1-5 & 8-12	20 mg SC twice daily days 1-5 & 8-12
0	200 mg PO once daily days 1-5 & 8-12	20 mg SC twice daily days 1-5 & 8-12
1	250mg PO once daily days 1-5 & 8-12 ¹	20 mg SC twice daily days 1-5 & 8-12
2	300 mg PO once daily days 1-5 & 8-12	20 mg SC twice daily days 1-5 & 8-12

¹ AraC dose is a fixed dose of 20 mg s.c. per a single dose twice daily.

² AZD1775 should be taken either 2 hours before or 2 hours after a meal.

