Despite a lack of a clear biomarker/ PD marker for WEE1 kinase inhibition, based on preclinical data an effective pharmacological dose is up to the range of 750 nM, possibly higher to maximally 1000 nM. From recent PK data (REFMAL 984 and NCI study), daily dosing for 5 days for one or two weeks with AZD1775 was determined as the RP2D, that yielded an AUC (0-8 hrs) of ~8000nM. Therefore we would expect that 300mg AZD1775 daily would yield around 600-800 to maximally 1000 nM concentrations of AZD1775 in the first 8 hours.

For the combination arms (Arms A and B) in the Escalation portion we will escalate dose starting at AZD1775 200 mg daily on a 5-2-5 schedule. We will escalate up to/ until

- a) the current MTD/ RP2D of 300 mg daily (5-2-5 schedule) is reached at acceptable toxicity (AEs) regardless of preclinical PK efficacy
- b) DLT defining toxicities/ AEs are observed
- c) clinical efficacy is observed that would meet the primary response endpoint already below the current RP2D of 300 mg AZD1775 daily
- d) Clinical PK (AUC) of AZD1775 reaches approx. > 1000 nm/ hr

We will accomplish above goals with real-time assessment of safety, efficacy, PK and/or PD in each cohort.

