7.5 MTD Determination

This MTD determination applies to the Safety Portion. MTD for the safety portion will be defined as the dose level below the lowest dose that induces dose-limiting toxicity in at least one-third of subjects (at least 2 of a maximum of 6 subjects).

- 7.51 Three subjects will be treated at a given dose level combination and observed for one cycle to assess toxicity (accrual will be suspended while the 3 subjects are treated and observed – only applicable to the dose escalation cohort/ part of study).
 - 7.52 If DLT is not seen in any of the 3 subjects or in 1 of 3 subjects, 3 new subjects will be accrued and treated at the same dose level (accrual will be suspended while the 3 subjects are treated and observed). If DLT is seen in 2 or 3 of 3 subjects treated at a given dose level, then the next 3 subjects will be treated at the next lower dose level, if only 3 subjects were enrolled and treated at this lower dose level.
 - 7.53 After enrolling 6 subjects on a specific dose level, if DLT is observed in 1 or less subjects, then the combination dose will be considered safe for the expansion phase. If DLT is observed in at least 2 of 6 subjects, then the MTD will have been exceeded and defined as the previous dose unless only 3 subjects were treated at the lower dose level. In that case, 3 additional subjects will be treated at this lower dose level.
 - 7.55 If a subject fails to complete one cycle of treatment for reasons other than dose-limiting toxicity defined adverse events, the subject will be regarded as non-informative for estimating the MTD and an additional subject will be treated at the current dose level.
- 7.6 Dose escalation (inpatient) will not be allowed for a subject.
- 7.7a For this protocol, the subject must return to the consenting institution for evaluation at least once per cycle.
- 7.7b Local Medical Doctor (LMD)
When it has been determined that a patient's malignant disease is stable or objective tumor regression has been observed and the patient is tolerating therapy without excessive toxicity, after the first cycle of treatment, the standard of care drug AraC may be administered by the patient's Local Medical Doctor

(LMD). However, study drug AZD1775 can only be dispensed by an investigator or investigational site of the study. The registering physician retains responsibility for the patient.

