16.7 Early Safety Analysis

An early safety analysis will be performed after 6 patients have been accrued to each arm of the study and observed for one cycle. Accrual will be temporarily halted while these patients are evaluated. If 2 or more of the first 6 patients experience a DLT, as defined below, then the dose level will be reduced as defined in Section 8.0 and another six patients will be treated. If $< 2/6$ patients experience toxicities defined as DLT, then this dose level will be defined as the operational MTD and moved into the expansion portion. Further dose de-escalation to dose level -2 will follow the same guidelines.

Should additional modification be necessary, the study will be closed and evaluated by the study team regarding continuation. Upon determination of the safe dose level, the study will re-open for accrual.

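### Section 16.3 counts six MTD patients in Arm A and six in Arm B, but 7.21 gives the two arms one shared escalation; if 7.21 and the 16.21 MTD condition govern, the stated numbers yield 35 to 39 evaluable patients against 41 needed

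*Combined protocol and SAP*

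**What the plan says.** **Accrual.** Section 16.3 states that "Six patients in each of the safety arms will be treated at the MTD and thus will be eligible for primary endpoint analysis". It adds 15 expansion patients in Arm A and 14 each in B and C, plus two reserves per arm. It expects 18 safety patients, possibly up to 54, and a final total between 67 (23/22/22) and 102, apart from the 7 MF patients.

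**Run-in, six per arm.** The early safety analysis in 16.7 comes "after 6 patients have been accrued to each arm of the study". The dose there moves only downwards: "If 2 or more of the first 6 patients experience a DLT, as defined below, then the dose level will be reduced", with level -2 the last step. Section 1.5 also has six patients in each of three arms.

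**Run-in, shared escalation.** Section 7.21 draws cohorts of three from either combination arm and escalates from level 0 to level 2. Its NOTE says that escalation and MTD determination for Arms A and B "as outlined above will be performed together with patients from both Arms eligible". At the top level, "If there are no DLTs in the first 3 patients at dose level 2, an additional 3 patients will be treated".

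**Other run-in passages.** Section 7.52 uses a different cohort rule: "If DLT is not seen in any of the 3 subjects or in 1 of 3 subjects, 3 new subjects will be accrued", at the same dose level. Section 7.22 speaks of safety portions for both arms and lets their expansion doses differ. The Schema and 6.0 can be read as six combination patients in total. Section 3.12 lists only untreated elderly poor-risk AML under the combination's escalation part.

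**Evaluability and caps.** Section 16.21 requires treatment to have begun at the study MTD. The definitions in 16.22 and 16.23 omit that condition. Both sections call 23 and 22 the maximum accrual for their arms.

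**The concern.** The decision rules are fixed counts: at least 6 responders in 21 (Arm A) and at least 3 in 20 (Arms B and C). The power tables hold only at those sample sizes. Section 16.3 reaches them by crediting A and B with six MTD patients each, and a shared escalation supplies six between them. If accrual followed the stated 15/14 plus reserves, at least one of the two arms would fall short at the selected dose, and an active regimen would be more likely to be dropped. The gap could be filled by counting patients treated at other doses, which 16.21 excludes and 16.22/16.23 do not. The primary denominator therefore depends on which passage is followed.

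**Working it through.** **1. Reproduce the plan's figures.**
- Evaluable: A 6+15 = 21; B and C 6+14 = 20. With reserves: 23, 22, 22.
- Low total: 18 + (15+14+14) + 6 = 67.
- Safety maximum under 16.7: 3 arms × 3 levels (start, -1, -2) × 6 = 54. Section 7 reaches at most 48 (A/B 4 levels × 6 = 24; C 4 levels × 6 = 24).
- High total: 54+43+6 = 103; 16.3 says 102.
- Exact binomial power: A, P(X≥6 | 21, 0.40) = 0.904; B, P(X≥3 | 20, 0.25) = 0.909. Type I error is 0.083 and 0.075. The plan's tables agree.

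**2. Which figures separate the schemes.** The totals 18 and 67 do not. With no DLTs, 7.21 treats 3+3+6 = 12 A/B patients and 7.31 treats 6 in Arm C, so 12+6 = 18 and 18+43+6 = 67. What fits 16.7 and 1.5 but not 7.21 is six at the MTD in each safety arm, and the 54.

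**3. Evaluable count with a shared run-in and the 16.21 condition.** The paths of 7.21 and 7.5 were enumerated as a 3+3 over levels -1 to 2. Every path that ends in an MTD leaves six A/B patients at that level, with 6 to 24 treated in the A/B run-in. Hence:
- 6+15+14 = 35 without reserves
- 35+4 = 39 if every reserve is evaluable
- needed: 21+20 = 41

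The gap is 6, or 2 at best. If k of the six are in Arm A, then A = 15+k and B = 20-k without reserves. With reserves, A = 17+k and B = 22-k. Without reserves, A reaches 21 only at k = 6, where B = 14. With reserves, A needs k ≥ 4 and B needs k ≤ 2. No split meets both targets.

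**4. Power if accrual stops there, cut-offs unchanged.** No passage fixes the split.

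| Case | Arm A: n, power at 40% | Arm B: n, power at 25% |
|---|---|---|
| Stated | 21, 0.90 | 20, 0.91 |
| Even split, no reserves | 18, 0.79 | 17, 0.84 |
| Even split, all reserves | 20, 0.87 | 19, 0.89 |
| All six in A, no reserves | 21, 0.90 | 14, 0.72 |
| All six in B, no reserves | 15, 0.60 | 20, 0.91 |

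Type I error at the even split without reserves is 0.042 (A) and 0.050 (B).

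**5. If the 23 and 22 caps bind.** They allow 23+22 = 45 A/B patients. On a shared path with six patients treated off the MTD, 45-6 = 39 are at the MTD. Two examples:
- No DLTs up to level 2: 3+3 patients are below the MTD.
- 0/3, 0/3, then at least 2/3 DLTs at level 2 and three more patients at level 1: three are below the MTD and three above it.

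Longer paths leave fewer. The longest enumerated path treats 24, six of them at the MTD, and leaves 45-18 = 27. Shorter paths suffice: none off the MTD leaves 45, three leave 42.

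**The case against.** The best defence is that the shortfall needs two conditions together, and the documents offer alternatives to each.

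- **Separate run-ins.** Section 1.5 gives six patients to each arm, and 7.22 suggests separate safety portions. Then 12+29 = 41, and 16.3 is right.
- **No MTD condition.** The definitions beside the decision rules, in 16.22 and 16.23, do not require the MTD. On the path without DLTs, 12+29 = 41 again. This rescue is partial: a shared run-in of only six patients gives 6+29 = 35.
- **Accrual by target.** Section 16.22 judges the first 21 evaluable patients and 16.23 plans 40 evaluable. If accrual runs to those numbers, the stated power stands. The range in 16.3 has room: closing the gap on the path without DLTs takes 12+35+4+22 = 73 patients, well below 102.

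All three points stand, and they make the power loss conditional. They do not settle which passage governs.

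The even split is also only an illustration. Read literally, 3.12 would put all six shared patients in Arm A, leaving B with 14 before reserves. The list layout in the extracted text is too uncertain to rely on for that.

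Three stronger readings are tempting. A reader might infer that 18 and 67 are wrong under 7.21; they are not, as step 2 shows. A reader might infer that the trial is underpowered; that follows only if accrual stops at the stated numbers or the caps bind on a path like those in step 5. A reader might fear more false positives; type I error falls with smaller n.

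**Conclusion.** The inconsistency holds and should be fixed. The claim in 16.3 of six MTD patients in each safety arm matches 1.5 and 16.7 but not the joint escalation of 7.21. With a shared run-in and the 16.21 condition, A and B are 2 to 6 evaluable patients short of 41. This assumes that the run-in ends with six A/B patients at one shared MTD. Section 7.4.b also allows escalation to stop for efficacy or exposure without saying how many patients must then be at the chosen level.

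At an even split, the loss in power is 0.03 to 0.11 in Arm A and 0.02 to 0.07 in Arm B, and only if accrual stops early. Independently of that, 23 and 22 cannot be both the maximum for their arms and the low end of a range reaching 102. Both defects concern how accrual and evaluability are specified; neither undermines the decision rules.

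**What to change.** 1. Reconcile the Schema, 1.5, 3.12, 6.0, 7.21, 7.22, 7.5, 16.3 and 16.7 on whether the A/B run-in is shared and how it proceeds. The choice of clinical rule belongs to the investigators and sponsor.
2. Use one evaluability definition in 16.21, 16.22 and 16.23, and say explicitly whether treatment must have begun at the MTD.
3. In 16.3, replace the fixed 15/14/14 with accrual until 21 (A), 20 (B) and 20 (C) patients are evaluable under that definition, or restate power for the n that results.
4. State whether the 23/22/22 caps exclude run-in patients not treated at the MTD, and make the maximum in 16.22/16.23 agree with the range in 16.3.
5. Recompute the upper total: the present parts give 103, and 54 itself depends on item 1.

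The cost is wording and possibly a higher stated accrual. With a shared run-in, the MTD condition and no DLTs, the low total would rise from 67 to 73, apart from MF patients. The 21/20/20 targets and the 6/21 and 3/20 cut-offs do not change.
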